9. RESEARCH METHODS

9.1 Study design

The study will be performed using a non-interventional longitudinal population-based retrospective cohort design. It will be conducted using secondary data derived from multiple databases in Denmark, Finland, France, Germany, and USA. The unit of analysis is individual pregnancies in women with moderate/severe SLE. Therefore, each woman may contribute multiple occurrences of pregnancies to the study.

There are two primary outcomes of interest: **composite of MCM** and **select pregnancy loss outcomes**. The ascertainment period for MCM is from the end of the pregnancy until one year of age, while the ascertainment period for select pregnancy loss outcomes is from LMP2 until end of pregnancy. The study design schemas for these outcomes are provided in Figure 1 (MCM) and Figure 2 (select pregnancy loss outcomes) below.

The secondary outcomes of interest are mCM, adverse pregnancy outcomes, and adverse birth outcomes. The outcome ascertainment periods for these secondary outcomes are from birth until one year of age (mCM), from LMP2 until end of pregnancy (adverse pregnancy outcomes) and at birth (adverse birth outcomes). The study design schemas are presented in Figure 1 (mCM), Figure 2 (adverse pregnancy outcomes) and Figure 3 (adverse birth outcomes).

The exploratory outcomes of interest are adverse outcomes related to infant growth. The ascertainment period for this outcome is from birth until 1 year of age. The study design schema is presented in Figure 4. In addition to this exploratory outcome, analysis for the select pregnancy loss outcome (composite of spontaneous abortion and stillbirth) by specific trimester of anifrolumab exposure (details as provided in Section 9.3.1), and the risk of MCM by target body organ system classification according EUROCAT (41) will be conducted.

For congenital malformation (CM), birth and infant outcomes, the population of study will be limited to offspring for whom mother-offspring record linkage is available within each data source. However, for pregnancies that end in a spontaneous abortion, an elective termination of pregnancy or stillbirth where there is a diagnosis of MCM, mother-offspring linkage will not be required.

The exposure of interest is *in utero* exposure to anifrolumab (see Section 9.3.1) and/or *in utero* exposure to SLE SOC between last menstrual period + 2 weeks (LMP2) (derived from last menstrual period or, if missing, gestational age) and:

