- g. Exposure to SLE SOC will be assessed in the exposed and comparator groups at LMP2 with a look-back period of 5-half-lives of relevant drug. Exposure to anifrolumab will be assessed from LMP2 until end of the first trimester of pregnancy for MCM outcome and anytime during the pregnancy for mCM outcome with a maximum look-back period of 16-weeks (time for anifrolumab concentration to fall below the LLOQ for 95% of patients) prior to LMP2
- h. Comorbidities and covariates measured during pregnancy may include maternal smoking, alcohol and substance abuse, gestational diabetes
- i. First of the following: diagnosis of CM, death, emigration, end of study period (reaching the age of 1 year), and administrative data cut off
- j. Covariates measured at index date may include maternal socioeconomic status (SES), age at LMP2

[figure not shown]

Figure 2: Overview of the study design, for adverse pregnancy outcomes

- a. Diagnosis of SLE before pregnancy
- b. Women with a continuous enrolment in the database for ≥ 12 months prior to conception (defined as LMP2)

- c. Singleton pregnancy, mother-offspring linkage. Mother-offspring linkage will be required for ectopic pregnancy, spontaneous abortion, elective termination, stillbirth, infections requiring hospitalisation, caesarean section
- d. Women with a history of CM or chromosomal abnormalities
- e. Pregnancy associated with in vitro fertilisation (IVF), date of conception cannot be established
- f. Comorbidities and covariates measured prior to index date may include maternal diabetes, maternal pre-pregnancy BMI, obstetric history
- g. Exposure to SLE SOC will be assessed in the exposed and comparator groups at LMP2 with a look-back period of 5-half-lives of relevant drug. Exposure to anifrolumab will be assessed from LMP2 until end of pregnancy with a maximum look-back period of 16-weeks (time for anifrolumab concentration to fall below the LLOQ for 95% of patients) prior to LMP2
- h. Comorbidities and covariates measured during pregnancy may include maternal smoking, alcohol and substance abuse, gestational diabetes

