9.2.2 Participants

To address the research questions, eligible cohorts will be identified through a nested selection process (Figure 5). An *overall source population* will be created for data extraction (STEP 1) and split into *exposed to anifrolumab source population* and *unexposed to anifrolumab source population* (STEP2).

Then criteria common to exposed and unexposed to anifrolumab source populations will be applied to create post-data extraction *exposed to anifrolumab study population* and *unexposed to anifrolumab study population* (STEP 3) from where the cohorts of analyses will be derived (STEP 4).

Since this is a non-interventional observational study, minimal inclusion and exclusion criteria are desirable to minimise potential selection bias and represent real world clinical practice.

STEP 1

Inclusion criteria for data extraction to create an *overall source population*:

- Singleton³ pregnancies
- Women diagnosed with SLE

Exclusion criteria for data extraction to create an *overall source population*:

- Pregnancy associated with in vitro fertilisation (IVF)⁴

STEP 2

Step to create *exposed to anifrolumab source population* and *unexposed to anifrolumab source population*, from the overall source population (created in STEP 1).

STEP 2A - exposed to anifrolumab source population

Additional inclusion criteria to be applied after data extraction to create an *exposed source population*:

- Women with a continuous enrolment⁵ in the database for ≥ 12 months prior to LMP2
- Women diagnosed with SLE before pregnancy
- Women exposed to anifrolumab (polytherapy, added to SLE SOC) during pregnancy and/or 16-week period prior to LMP2⁶

Additional exclusion criterion to be applied after data extraction to create an *exposed source population*:

- Pregnancies whose date of conception cannot be established

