Exposure to co-medications in the 16 weeks prior to LMP2 will be investigated and considered as a risk factor for the primary and secondary outcomes. A polypharmacy index will be created. There is no consensus definition of polypharmacy (72). In this study, polypharmacy will be considered as a continuous variable, reflecting the cumulative number of the prescribed medications from other therapeutic classes (other than those specified for the treatment of SLE described in Section 9.3.1), within an interval of interest. This polypharmacy index will be considered for confounding adjustment. The rationale for considering polypharmacy as a potential risk factor is based on some evidence that polypharmacy may be associated with adverse events during pregnancy. Factors which may contribute to the foetal risk in polypharmacy include the pathophysiology of the underlying co-morbid conditions, adverse drug effects and the potential for drug-to-drug interaction (72, 111). In addition, polypharmacy may be an indication of severity of disease, with SLE manifestations in multiple organ systems requiring treatment (102).

Maternal age at conception. Maternal age at conception is considered a major risk factor for the studied outcomes. Multiple epidemiological studies have found a relation between advanced maternal age at conception and congenital malformations (57), adverse pregnancy (46), birth and infant outcomes (52). Although maternal age is not directly associated to the exposure of interest, it is associated with the severity of the disease and with the selected outcomes, thus this variable will be considered for confounding adjustment.

Gestational age. Is measured from the first day of the LMP and expressed in weeks and days, completed weeks, or in days. Gestational age is usually calculated from the reported LMP (depends on recall of the LMP and assumes that ovulations occurred on average 2 weeks after LMP). If gestational age is calculated from LMP, 2 weeks will be added to the time interval to estimate the conception date (LMP2). For data sources in which the LMP is missing, date of conception (equivalent to LMP2) will be estimated based on date of birth and gestational age at birth. In

countries where gestational age is calculated from conception, gestational age (in days) will be subtracted from the date of birth to obtain the date of conception.

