Foetal biometric measures from ultrasounds are increasingly being used to confirm or adjust LMP. Current recommendations from the American College of Obstetricians and Gynaecologist, the Society for Maternal-Foetal Medicine, Euro-Peristat Network recommend use of the best obstetric estimate rather than LMP alone. Hence, in Europe, and USA, estimate of gestational age is based on ultrasound dating, and rarely based on LMP alone due to reporting errors (23). Thus, gestational age will be assessed using the best obstetric estimate available. Gestational age is rarely available for ectopic pregnancies or miscarriages.

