9.5.1.1 Assumptions used for the sample size and power calculations

To estimate the number of anifrolumab exposed SLE pregnancies and the expected number of primary study outcome events in data sources that would be eligible for the analysis in this study, the following assumptions were used:

- **A prevalence of 7% for MCM outcome.** Prevalence of MCM in pregnancies in women with moderate-to-severe SLE was estimated based on a literature search. Among moderate/severe SLE patients exposed to belimumab, birth defect prevalence estimates of 5.6% to 21.7% were observed in post hoc summary of clinical studies and a prospective

pregnancy registry, respectively (86) A prevalence of 6.4% of congenital malformations was observed in renal SLE pregnancies (51) These proxy estimates of MCM in moderate-to-severe SLE align with the observed population based prevalence estimates ranging from 7.4% to 13.6% (114) among women diagnosed with SLE (117).

- **A prevalence of 20% for the composite of select pregnancy loss outcomes (composite of spontaneous abortion and stillbirth).** Prevalence of the composite outcome of select pregnancy loss (spontaneous abortion and stillbirth) in moderate-to-severe SLE pregnancies ranged from 15.3% to 30% (51, 81, 86). For the individual outcomes, the prevalence estimates ranged from 1.8% to 3.7% for stillbirths (51, 103, 120), and the prevalence estimate was 16% (12.1% to 19.9%) for spontaneous abortions (103). Based on the intended objective to evaluate embryo-foetal loss, a composite outcome of spontaneous abortion and stillbirth has been used.
- **Proportion of SLE pregnancies occurring in women with moderate-to-severe disease of 50%.** There is limited information on the proportion of SLE pregnancies that occur in women with moderate-to-severe disease. The proportion of moderate-to-severe disease at the time of diagnosis among the general SLE population is estimated to be 50% (66, 80). Literature regarding medication patterns for SLE pregnant women suggests that 40-45% use immunosuppressors and/or biologics, which may be a proxy indicator of moderate/severe disease (12, 67). Thus, in this study, an assumption of 50% was used.

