² Not captured by claims but will be calculated using an algorithm for gestational age which prioritizes the week of gestation using Z3A% codes-ICD-10CM (primary approach). Single Z3A ± 3 days of the estimated delivery date is preferred, followed by at least two Z3A codes within a lookup period that represent a distinct pregnancy in a monotonically decreasing order. If Z3A codes are not available, other codes with a range of gestational age (GA) are used, with codes indicating a specific GA or longer GA being given priority. An approximate midpoint of GA +4 days is applied for codes with the GA range. If no codes indicating GA are found, a fixed GA is assigned based on trimester or term status (61).

³ The potential age at conception can be calculated based on the delivery and mother's birth date.

⁴ Code Z68 is introduced in the ICD-10 version of medical claims, so it is possible to obtain it from the claims for 2015 and onwards.

⁵ Can be derived from weight and height, but completeness is unknown.

⁶ Available if hospital visits with ICD-10 code as main reason.

⁷ Previous spontaneous abortion is only captured (in NPR) if the patient is in contact with a hospital regarding this. This information is not available if only a GP or a specialist in private practice (e.g., gynaecologist) is contacted regarding this because diagnoses are not available. For that reason, many early spontaneous abortions will not be captured.

⁸ Available (amount available in Medical Birth Register, Register of Congenital Malformations and Register of Induces Abortions. Available in HILMO and AvoHILMO if ICD-10 code was the main reason for health care visit).

⁹ No information was provided by the data source.

¹⁰ Testing for antinuclear antibodies, anti-dsDNA antibodies, anti-Smith antibodies, complement proteins (C3, C4, CH50) or blood panel including kidney function tests.

¹¹ Available, if ICD-10 code was the main reason for health care visit.

¹² Available if coded during visits but it is unknown to the level of completeness or availability.

¹³ Only partially available since women are either enrolled when they want to conceive or when they are already pregnant.

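### The conception-date exclusion may remove a large, unquantified and source-dependent share of miscarriages, the main part of the second primary outcome; Figure 2 note c separately contradicts the linkage rule

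*Protocol*

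**What the plan says.** **Exclusion.** Section 9.2.2 removes, in both the exposed (Step 2A) and unexposed (Step 2B) source populations, "Pregnancies whose date of conception cannot be established".

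**How conception is dated.** Section 9.1 says that LMP2, the conception date, is "derived from last menstrual period or, if missing, gestational age". For sources without LMP, Section 9.3.3 (Gestational age) says that "date of conception (equivalent to LMP2) will be estimated based on date of birth and gestational age at birth". The same subsection says that dating in Europe and the USA rarely rests on LMP alone, and it ends: "Gestational age is rarely available for ectopic pregnancies or miscarriages".

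**The one written fallback.** Table 17, footnote 2 (Appendix C) describes the Carelon algorithm: "If no codes indicating GA are found, a fixed GA is assigned based on trimester or term status". No comparable rule is written for the other five sources.

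**The outcome.** Section 9.5.1.1 assumes "A prevalence of 20% for the composite of select pregnancy loss outcomes". It cites 16% (12.1 to 19.9%) for spontaneous abortion and 1.8 to 3.7% for stillbirth.

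**Linkage.** Figure 2 is the schema for pregnancy outcomes, including this primary one. Its note c says: "Mother-offspring linkage will be required for ectopic pregnancy, spontaneous abortion, elective termination, stillbirth, infections requiring hospitalisation, caesarean section". The Abstract and Section 9.1 confine the linkage requirement to malformation, birth and infant outcomes. Table 3 gives the population as all pregnancies, and Table 5 sets no linkage criterion for the pregnancy cohort.

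**The concern.** A live birth or stillbirth has a birth date and usually a gestational age, so it can be dated and stays in. A miscarriage has no birth date, and by the protocol's own statement rarely a gestational age. If LMP is also missing, it leaves both numerator and denominator. Selection then depends on the outcome, within the component that supplies most of the events.

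Embryo-foetal loss is the non-clinical signal behind the study (Sections 7.4 and 7.5) and the stated reason for choosing this composite (Section 9.5.1.1). A rule that removes such losses lowers the absolute risk reported under Objective 3. It can also pull the Objective 4 RR towards that of stillbirth alone, to a degree that varies between sources entering one meta-analysis.

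Neither the study size nor the limitations allow for this. Section 9.5.1.2 counts all pregnancies outside the two US sources as eligible. Section 9.9 treats conception dating as an error of days for most patients and expects little misreporting of spontaneous abortion, but does not mention this exclusion.

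**Working it through.** **1. The plan's own figures.** With margin RR 2.5, true RR 1, one-sided alpha 2.5%, 80% power, risk p = 0.20 and k comparators per exposed pregnancy, the Poisson variance gives

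n exposed = (1.960 + 0.842)² × (1 + 1/k) / (p × (ln 2.5)²)

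This is 71 for 1:2 and 63 for 1:3, against 72 and 61 in Section 9.5.2. Simulating the protocol's fixed-effect procedure (20,000 runs) gives 81.5% power at 25/25/22 exposed (1:2), 79.3% at 21/21/19 (1:3), and above 99% at 163/162/11/145. The stated figures reproduce, and they use the full 20% risk.

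**2. Weight of miscarriage in the composite.** 16 / (16 + 3.7) = 81%; 16 / (16 + 1.8) = 90%.

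**3. Observed risk.** Let q be the share of spontaneous abortions that cannot be dated, equal in both groups. The documents do not give q, so a range is shown. Assume 17% spontaneous abortion and 3% stillbirth (sum 20%).

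Observed risk = (0.17(1 − q) + 0.03) / (1 − 0.17q); share of events lost = 0.17q / 0.20

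| q | Observed risk | Events lost |
|---|---|---|
| 0 | 20.0% | 0% |
| 25% | 0.1575 / 0.9575 = 16.4% | 21.3% |
| 50% | 0.1150 / 0.9150 = 12.6% | 42.5% |
| 75% | 0.0725 / 0.8725 = 8.3% | 63.8% |
| 90% | 0.0470 / 0.8470 = 5.5% | 76.5% |

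Stillbirths outnumber the remaining abortions only if 0.17(1 − q) < 0.03, that is q above about 82%.

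**4. Effect on the RR.** As an illustration, suppose exposure doubles spontaneous abortion (16% to 32%) and leaves stillbirth at 4%. The true composite RR is 0.36 / 0.20 = 1.80. The observed RR is:
- q = 50%: (0.20/0.84) / (0.12/0.92) = 1.83
- q = 90%: (0.072/0.712) / (0.056/0.856) = 1.55
- q = 100%: (0.04/0.68) / (0.04/0.84) = 1.24

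Attenuation appears only when most miscarriages are lost.

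**5. Power.** Simulated with 16.3% abortion, 3.7% stillbirth and 1:2 allocation, in the sources the protocol expects to contribute (481 exposed at 10% uptake, 236 at 5%):

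| q | Observed risk | Required exposed | Power, 10% uptake | Power, 5% uptake |
|---|---|---|---|---|
| 50% | 12.9% | 109 | >99% | 99% |
| 90% | 6.3% | 225 | 97% | 72% |
| 100% | 4.4% | 318 | 87% | 47% |

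If Carelon keeps all its miscarriages and the other sources lose all of theirs, closed-form power is above 99% and about 94%. The worst corner is stillbirth at 1.8% with every miscarriage lost, where power is 44% and 8%.

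**6. Linkage.** Section 9.4.1 limits linkage to live births and stillbirths after 22 weeks in Denmark, to the same or a birth weight over 500 g in Finland, and to live births and stillbirths in France. European spontaneous abortions are defined as under 22 weeks (Section 9.3.2). In those sources a linkage requirement for spontaneous abortion cannot generally be met.

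**The case against.** The exclusion is triggered by a missing conception date, not by missing gestational age alone. LMP comes first, and nothing in the protocol says that LMP is absent for miscarriages. Table 17 lists age at conception as available in DAPI, Denmark, France and RHEKISS and partly in Finland. RHEKISS enrols by week 20 at the latest and reports each trimester. The follow-up limits for spontaneous abortion and ectopic pregnancy in the Section 9.3.2 footnotes presuppose that losses are dated, with details left to the statistical analysis plan. LMP2 also anchors the 12-month enrolment rule, the 16-week exposure window and the severity assessment, so excluding undatable pregnancies has a reason.

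Most of this stands, and it rules out stronger readings. A reader might infer that the rule deletes miscarriages, that Objective 4 becomes mainly a stillbirth comparison, or that power collapses. The documents give no undatable share. The second reading needs more than about 82% lost, and at 50% lost power is still about 99% or better.

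It does not remove the point. Table 17 is not specific to losses. In Appendix C the Nordic LMP data sit in the birth registers, which by Section 9.4.1 hold births and stillbirths (22 weeks or more in Finland). Table 15 lists French LMP among maternity data alongside delivery and birth items. A derivation algorithm can wait for the analysis plan; a stated eligibility rule that conflicts with the protocol's own account of the data cannot.

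Note c is probably a dropped negative. It does not show that all spontaneous abortions will be lost, because Section 9.1 and Table 5 say otherwise.

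**Conclusion.** The point holds as a conflict between an eligibility rule, a birth-based fallback and the protocol's own statement on data availability. The rule may remove a large share of miscarriages; how large is unknown and will differ by source. Under the 17% plus 3% assumption, with the same undatable share in both exposure groups, the Objective 3 risk would read 16.4% at a quarter lost and 5.5% at nine tenths lost, instead of 20%. The Objective 4 RR may be attenuated if most miscarriages are lost; at half lost the illustration shows none. Power is secondary and becomes a concern only towards near-complete loss, chiefly at 5% uptake. Note c is a separate and plain contradiction. Confidence is high on the conflicts and low on the size of the effect.

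**What to change.** Set one LMP2 hierarchy for all pregnancies, in all six sources and identically in both exposure groups: recorded LMP or ultrasound estimate, then gestational-age codes, then an assigned outcome-specific gestational age, extending what Carelon already does. Exclude only pregnancies still undatable after that, whatever their outcome. Waiving the exclusion for losses alone would again make eligibility depend on the outcome, this time inflating the risk.

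Report exclusions by outcome and source. Add a sensitivity analysis that shifts the assigned gestational age, and one restricted to pregnancies with recorded dating. Correct Figure 2 note c to say that linkage is not required, and name the exclusion in Section 9.9. The same hierarchy serves the secondary ectopic-pregnancy and foetal-loss outcomes.

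The cost is protocol and analysis-plan wording, one dating algorithm per source, and some exposure-dating error among losses with an assigned gestational age, which the sensitivity analyses are there to show.

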9.4 Data sources

A feasibility assessment was conducted between June 2022 and January 2023 to assess the suitability of the proposed data sources to address this study's research question and objectives. Information was collected from the data source holders and supplemented by desktop research. Data sources from eight countries (Denmark, Finland, France, Germany, Spain, Sweden, UK, USA) and four SLE specific registries (SLE Registry Germany, Spanish Society of Rheumatology systemic lupus erythematosus registry [RELESSER], OM1 Lupus Registry and The Systemic Lupus Erythematosus International Collaborating Clinics [SLICC]) were assessed in the feasibility assessment. Of these data sources, six were selected: Carelon Research (USA), DAPI (USA), Finnish National Registries, Danish National Registries, SNDS (France), RHEKISS (Germany). A summary of the rationale for inclusion/exclusion of each data source evaluated in the feasibility assessment is presented in Table 14 of Appendix C. Data sources were selected based on the ability to capture anifrolumab and SLE SOC use, the study outcomes and the potential size of the study population. The following information were collected on each data source during the feasibility assessment:

- Characteristics of the data source
- Access requirement
- Availability and coding systems of drugs, medical diagnoses, procedures and laboratory measurements
- Availability and completeness of variables (exposure, outcomes and covariates)
- Estimated number of pregnancies occurring in SLE patients
- Estimate of number of pregnancies in SLE patients who were prescribed anifrolumab in the preceding 12 months (applicable for USA data sources only)

As anifrolumab was granted market authorisation in the EU in 2022 and approved in the USA in 2021, information on the availability of anifrolumab use is limited or unavailable in some data sources. Due to the limited availability of information on anifrolumab exposure data, exposure to biologics indicated for a similar population and with a similar administration route (belimumab IV

infusion) was used as a proxy to evaluate the ability of the data source to capture anifrolumab exposure when it becomes available in the respective countries.

Considering the estimated sample size required for this study, it is estimated that the selected data sources will provide a sufficient sample size to address the research questions (see Section 9.5). If it is determined at the time of interim reports, that the selected data sources will not provide the required sample size, mitigation approaches will be considered. These mitigation approaches include the use of additional data sources (which were deemed feasible but not currently selected), and extension of the study period.

